9.0 Statistical Considerations

Power analysis: Our primary endpoints include apoptosis biomarkers (e.g. TUNEL and Bax), and expression of TRPM7, COX-2 (inflammation) and Ki-67 (proliferation index), pMLKL in colorectal mucosa as well as magnesium status (total erythrocyte magnesium, magnesium tolerance test), and urinary excretion of prostaglandin E₂ metabolite (PGE-M). No study has ever reported the effects of magnesium supplementation on the primary endpoints in the mucosa or any other tissues of the colorectum. Our study will be the first study of this kind. However, all the anti-carcinogenesis effect of magnesium supplementation will be related to the change in the level of body magnesium status. Therefore, we based our power analysis on the pilot data of total erythrocyte magnesium, one of the primary study endpoints.

We have conducted a pilot study of total erythrocyte magnesium with 50 colorectal adenoma cases and 50 matched controls. Presented in the table are the means and standard deviations by the *TRPM7* genotype among colorectal adenoma patients with a high dietary ratio of calcium to magnesium (ratio>2.6). Even with such a small sample size, we still found a statistically significant ($p=0.04$) difference in the mean of erythrocyte magnesium between the GG and the GA/AA combined group (only one subject with the AA genotype). On the other hand, we did not find a significant difference by genotype among adenoma patients with a low dietary ratio of calcium to magnesium. These results are consistent with those we recently reported on the interaction between calcium/magnesium intake ratio and the *TRPM7* polymorphism in relation to both colorectal adenoma and hyperplastic polyps (e.g. increased risk of colorectal adenoma associated with the GA or AA genotype only appeared in those with a high calcium/magnesium ratio, but not in those with a low ratio). Based on these findings, we expect the primary treatment effect (modulating high calcium/magnesium ratio from above 2.6 to below 2.6) will be a reduction in the difference in erythrocyte magnesium between genotypes. The normal reference range for erythrocyte magnesium is from 4.0 to 6.5 mg/dL. Thus, we expect treatment will increase the mean erythrocyte magnesium among the GA or AA group to the median mid-point of the normal range, (i.e. 5.25 mg/dL,) which is also the observed mean for the GG genotype group.

Since the study has a 2 by 2 factorial design, we calculated the study power based on an ANOVA model which has two factors: treatment (treatment vs. placebo) and genotype (GG vs. GA and AA combined). There are 4 groups with 60 patients each by study design. At a 5% two-sided significance level, a two-way analysis of variance will have 94% power to detect the main treatment effect, the main genotype effect, and their interaction, assuming that the common

Table D3. Mean (standard deviations) for total erythrocyte magnesium among colorectal adenoma patients with a high Ca/Mg intake ratio, according to the Thr1482Ile *TRPM7* polymorphism.

TRPM7 genotype	Ca/Mg intake ratio>2.6 (placebo)
GG	5.25 ± 1.16 (n=16)
GA/AA	4.49 ± 0.50 (n=7)
GA	4.61 ± 0.40 (n=6)
AA*	3.7 ± 0.40 (n=1)

* There is only one patient possessing the AA for Ca/Mg ≤2.6; thus, no standard deviations can be estimated. We used the standard deviations for the GA genotype in the power calculation.

standard deviation is 0.830 (average of 1.16 and 0.50). In this calculation, we expect both the treated GG genotype group and the treated A allele carrier (GA and AA combined) group will have mean total erythrocyte magnesium of 5.25 mg/dL. If we conservatively use a standard deviation of 1.16, the power will be 71%. This power calculation is conducted using nQuery®, a commercial software.

Base on our recently reported findings, the AA genotype would likely benefit the most from the magnesium supplementation. It is important to estimate the treatment effect within the three genotype groups and to compare the effects between the genotype groups. However, the AA genotype frequency is low (1.6%). We will be making every effort to enroll AA genotypes and expect to recruit 10 subjects during the 4 year recruiting period. Five each will be randomized to the treatment and the placebo group by stratifying on genotype groups. Due to the unequal number of subjects in the 2 by 3 ANOVA analysis, we conducted a simulation study to calculate the power for the interaction between the treatment and the GA genotype and the interaction between the treatment and the AA genotype. We used GG as the reference group. The power is 68% and 65%, respectively, with alpha=0.05. These separate powers are lower than the 0.94 power when GA and AA are combined since, besides the sample size difference, the simulation study allows us to use different standard deviations for the different subgroups of subjects, as opposed to a common standard deviation that has to be assumed by the method in the nQuery® software.

Data analysis plan: This study will adopt a 2X2 factorial design. The first factor is genotype (GG vs. GA/AA or GG vs. GA vs. AA) and the second factor is intervention (magnesium treatment: modulating dietary Ca/Mg intake ratio versus placebo). The primary endpoints, which are all continuous variables, include apoptosis biomarkers (e.g. TUNEL and Bax), and expression of TRPM7, COX-2 (inflammation) and Ki-67 (proliferation index), pMLKL in colorectal mucosa. The secondary endpoints include serum level magnesium, serum vitamin D, and plasma concentration of C-reactive protein as well as magnesium status (magnesium tolerance test), and urinary excretion of prostaglandin E₂ metabolite (PGE-M).

Standard graphing and screening techniques will be used to detect outliers and to ensure data accuracy. Distributions of continuous outcomes will be assessed for normality. If normality is violated, proper data transformation will be applied or non-parametric analysis methods will be considered. Summary statistics for both continuous (mean \pm standard deviation) and categorical variables (count and percent) will be provided by randomization groups to describe the study sample. Specific inferences on effects of interest will be made by reporting a point estimate along with a 95% confidence interval and the p value. Hypotheses will be tested at the level of $\alpha=0.05$. This data analysis plan will be carried out using statistical software SAS® (Cary, North Carolina) or statistical analysis package R (R Development Core Team, 2008). These basic statistical rules will be applied to all study aims.

Two-way ANOVA or ANCOVA analyses will be conducted to analyze the primary and secondary endpoints with intervention and genotype in the model (ANOVA) or other potential confounders including polyp type, size, and location for primary hyperplastic polyp or/and adenoma as well as body mass index, age, total energy intake, and intakes of other nutrients (average of six 24-hour recalls) in the model (ANOCOVA). Overall intervention effect and genotype effect and their interactions will be tested.

Univariate analyses will be conducted for these ten primary and secondary end points (continuous variables) in relationship to magnesium treatment and placebo using between-group t-test or non-parametric tests within genotype groups. The difference in the study endpoints (primary+secondary) between magnesium supplement and placebo will be estimated for the genotype groups (GG, GA, AA and GA and AA combined) along with their 95%

confidence intervals. The interaction between the genotype and intervention will be estimated as the difference of the within-genotype magnesium supplement versus placebo differences.

Administrative Interim analyses Administrative interim analyses may be performed as needed prior to the completion of the clinical trial over the 5 year period. One example of such administrative interim analyses is to generate preliminary data for a new grant submission. The study team does not have any intention to stop the trial at these interim analyses, thus there is no need to establish a stopping rule. A biostatistician from outside the study team will perform such analyses on unblinded data. All study team members remain blinded until the completion of the study. However, summarized study group-level data from such interim analyses may be communicated to the study PI's solely for the purpose of planning other studies.

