
This study will enroll 288 participants, 152 of whom have the GG genotype and 136 of whom have GA/AA genotype. Within the two genotype groups, a permuted-block randomization algorithm will be used to allocate the subjects into the treatment/placebo arm. These participants will be randomized to either treatment or placebo using a double-blind two-factorial (Ca/Mg intake ratio and genotype) design so that each treatment/placebo arm will contain 60 participants with the GG genotype and 60 participants with at least one A allele. (See details in Section 6.0)

Once our study is approved by Vanderbilt IRB, we will register our trial with [ClinicalTrials.gov](#) via a web based data entry system called the Protocol Registration System (PRS). Our trial will be registered in full not later than 21 days after the first patient is enrolled.

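### The 94% power averages SDs instead of variances and, on one consistent variance basis, falls to about 91% or about 81%; the powered endpoint also has no fixed tier

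*Combined protocol and SAP*

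**What the plan says.** The power analysis in section 9.0 explains that no data exist for the mucosal endpoints and continues: "Therefore, we based our power analysis on the pilot data of total erythrocyte magnesium, one of the primary study endpoints". For the 2x2 ANOVA it states "There are 4 groups with 60 patients each by study design", a two-sided 5% level, a mean of 5.25 mg/dL in both treated genotype groups, and a common "standard deviation is 0.830 (average of 1.16 and 0.50"). The result is 94% for the treatment effect, the genotype effect and their interaction, with 71% as a conservative case at SD 1.16. Table D3 gives means and SDs for untreated patients only: 5.25 ± 1.16 (GG), 4.49 ± 0.50 (carriers combined), 4.61 ± 0.40 (GA), and 3.7 with a borrowed 0.40 (AA). No SD is given for treated cells.

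For the 2x3 analysis: "The power is 68% and 65%, respectively, with alpha=0.05", for GA and AA in that order. The explanation is that "These separate powers are lower than the 0.94 power when GA and AA are combined", because of sample size and because "the simulation study allows us to use different standard deviations for the different subgroups of subjects". Those SDs are not listed. AA is 5 per arm; the GA number is not printed.

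On tiers, the same power section counts "magnesium status (total erythrocyte magnesium, magnesium tolerance test") and urinary PGE-M among the primary endpoints. Section 3.0 also calls magnesium status and PGE-M primary. Aim 1 in section 2.0, the analysis plan in section 6.0 (I. Data Analysis) and the analysis plan later in section 9.0 list six mucosal markers as primary, put PGE-M and the tolerance test among the secondary endpoints, and do not name erythrocyte magnesium.

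**The concern.** When cells are equal in size, the residual mean square estimates the mean of the cell variances. The square of a mean SD is always smaller than the mean of the squares when the SDs differ, and here they differ by more than a factor of two. The shortcut therefore understates the error and overstates power.

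The 2x3 figures raise a second doubt. If subgroup SDs were carried over from Table D3, the small carrier SDs should produce powers well above 68% and 65%. A reader cannot tell whether the two power statements describe the same trial under the same assumptions.

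At stake is whether the headline power can be relied on and reproduced, and whether the only endpoint with a power calculation has a defined place in the analysis.

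**Working it through.** **Inputs (section 9.0 and Table D3).** Placebo means: GG 5.25, carriers 4.49. Both treated means: 5.25. 60 per cell, residual df 236, two-sided 5%.

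**Contrasts.** Interaction: (5.25 − 4.49) − (5.25 − 5.25) = 0.76, with variance 4σ²/60. Treatment main effect: 5.25 − (5.25 + 4.49)/2 = 0.38, with variance 4σ²/240; the genotype main effect is the same size. All three share one noncentrality:

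λ = 0.76² × 60 / (4σ²) = 8.664/σ²

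Power comes from the noncentral F with 1 and 236 df.

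| Common SD | How obtained | λ | Power |
|---|---|---|---|
| 0.830 | (1.16 + 0.50)/2 | 12.58 | 94.2% (printed 94%) |
| 1.16 | plan's conservative case | 6.44 | 71.5% (printed 71%) |
| 0.893 | √[(1.16² + 0.50²)/2] | 10.86 | 90.7% |
| 1.035 | √[(3 × 1.16² + 0.50²)/4] | 8.08 | 80.8% |

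Both printed figures reproduce, so the set-up matches the plan's. The third row changes only the averaging and lets each treated cell keep its genotype's SD. The fourth gives treated carriers SD 1.16. Simulation with unequal cell SDs and a pooled error term agrees: about 91% and about 81% for all three effects.

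**2x3 analysis.** This was simulated with GG as reference and a pooled error term. Placebo means were 5.25/4.61/3.70 with SDs 1.16/0.40/0.40, and all treated means were 5.25. The GA cell is 60 carriers less 5 AA = 55 per arm. Treated-cell SDs are an assumption, shown as a range.

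| GG/GA/AA per arm | Treated-cell SDs | GA power | AA power |
|---|---|---|---|
| 60/55/5 | Table D3 (1.16/0.40/0.40) | about 80% | about 90% |
| 60/55/5 | 1.16 in every cell | about 65% | about 65% |
| 76/63/5 (all enrolled) | Table D3 | 86% | 90% |
| 76/63/5 (all enrolled) | 1.16 in every cell | 73% | 65% |
| printed | not stated | 68% | 65% |

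Table D3 SDs in both arms do not give the printed pair at either size. SD 1.16 in all treated cells comes close at the design size. That same assumption gives 81% in the 2x2, not 94%.

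**Tiers.**

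| Endpoint | Section 9.0, power analysis | Section 3.0 | Aim 1 and both analysis plans |
|---|---|---|---|
| Erythrocyte magnesium | primary | not named (magnesium status is primary) | not named |
| PGE-M | primary | primary | secondary |
| Tolerance test | primary | not named | secondary |
| Six mucosal markers | primary | some named, as primary | primary |

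The analysis plans speak of ten endpoints but name 11: six mucosal, plus serum magnesium, vitamin D, CRP, tolerance test and PGE-M.

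**The case against.** The plan declares 0.830 as an assumption, says how it was obtained, and prints a less favourable case. Both 91% and 81% lie inside its own 71% to 94% range. That stands, and it limits the weight of the point. It does not make 94% right for the SDs given.

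A reader might infer that 94% should simply be replaced by 91%. The documents do not support a single value, because 91% needs treated carriers to keep SD 0.50 and no treated SD is stated. Pooling the pilot SDs by degrees of freedom, √[(15 × 1.16² + 6 × 0.50²)/21] = 1.016, would give about 82%.

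The enrolment target is larger: "This study will enroll 288 participants, 152 of whom have the GG genotype and 136 of whom have GA/AA genotype". If all were analysed without loss (76 GG and 68 carriers per arm), the pooled SD would be √[(76 × 1.16² + 68 × 0.50²)/144] = 0.910 and power about 94% again. But section 9.0 states 60 per cell as its basis, and this figure also assumes SD 0.50 in treated carriers.

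A reader might also infer that the simulation certainly used SD 1.16 in treated cells. At 60/60/5 per arm that setting gives 67% to 68% for GA and 65% for AA, essentially the printed pair, but with 65 carriers per arm instead of 60. This is only a near match. The inputs are not in the text available, and the grant proposal listed as Appendix L may contain them.

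On tiers, it would go too far to say that the primary endpoints are undefined. The six mucosal markers are primary in Aim 1, both analysis plans and the power section. The Blood Draw Protocol does call erythrocyte magnesium primary, but for monitoring magnesium status and compliance, which is weak evidence of an efficacy tier. The count of ten probably predates the addition of pMLKL and is editorial.

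**Conclusion.** The point holds in limited form. At 60 per cell the printed 94% is too high on its own inputs: by about 3 points if treated cells keep their genotype's SD, and by about 13 points (94.2% − 80.8%) if treated carriers have SD 1.16. The 71% at SD 1.16 is correct. The 2x2 and 2x3 powers appear to rest on different variance assumptions; that is inferred from how far the figures are from agreeing, not from anything the plan states. All of this takes the Table D3 means and SDs and the treated mean of 5.25 as given.

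The tier conflict is confined to erythrocyte magnesium, PGE-M and the tolerance test, but it includes the one endpoint that carries the power calculation. No power is given for the six mucosal endpoints. None of this shows that the sample size is inadequate. It should be fixed, and the fix is cheap.

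**What to change.** 1. In the power analysis of section 9.0, state one set of treated-cell SDs and the GA cell size (55 per arm on the stated design), or cite where they are given.
2. Use averaged variances and recompute the 2x2 and 2x3 powers on that single basis. Restate the 94% in both places where it appears: about 91% with treated carriers at SD 0.50, about 81% with SD 1.16. Keep the 71%. If the 288 enrolled are the intended basis, say so and use those cell sizes throughout.
3. Use one endpoint list in sections 2.0, 3.0, 6.0 and 9.0, with erythrocyte magnesium, PGE-M and the tolerance test each in a single tier. Correct the count of ten to match: 11 as now named, 12 if erythrocyte magnesium is added.
4. Add a sentence that the power figures apply to erythrocyte magnesium only and not to the six mucosal primary endpoints.

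The cost is wording and one rerun of an existing simulation, with a less favourable printed 2x2 power. No patients, samples or visits are added.

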2.0 Rationale and Specific Aims

High intake of calcium, particularly when intake of vitamin D is also high, may protect against both colorectal cancer and adenoma, however, results have been inconsistent. Three recent studies have linked a high intake of magnesium to a significantly reduced risk of colorectal cancer. Nevertheless, one recent cohort study has not found such an association. We reported recently in the Tennessee Colorectal Polyp Study (TCPS; P50CA95103) that intake of magnesium is related to a significantly reduced risk of adenoma and hyperplastic polyps. This inverse association primarily appeared among those with a low ratio of calcium to magnesium intake (Ca/Mg intake ratio). We have found similar results for intake of calcium. Very recently, we have confirmed these novel findings in a large clinical trial study (unpublished results). Furthermore, in the TCPS, we found that the Ca/Mg intake ratio significantly interacted with the common Thr1482Ile polymorphism (rs8042919, G→A) of the *TRPM7* gene, in relation to both adenomas and hyperplastic polyps. The *TRPM7* gene is involved in calcium and magnesium re(absorption) and homeostasis. We also found the associations between intakes of calcium or magnesium and risk of colorectal adenoma and hyperplastic polyps may differ by the Thr1482Ile polymorphism. Therefore, our findings may partially explain the inconsistency in previous studies of the association of calcium and magnesium with risk of colorectal cancer or adenoma.

To follow-up on these novel and promising findings, we propose to conduct an intervention trial using biomarkers linked to colorectal carcinogenesis. In the proposed study, we will enroll 288 colorectal adenoma or/and hyperplastic polyp patients, polyps free participants but being at high risk of colorectal polyps or cancer from the TCPS study, the TIARS, Vanderbilt University Hospital, or from other resources, who consume a high dietary Ca/Mg intake ratio and whose daily calcium consumption is equal to or greater than 700 mg. Furthermore, these participants will be chosen from among those for whom Thr1482Ile polymorphism (G→A) genotyping was conducted in our previous and ongoing studies. We will enroll 152 who carry the GG genotype and 136 who possess at least one variant A allele (i.e. either GA or AA genotype), 10 of whom carry the AA genotype.

The **primary specific aims** of this study are to (*hypotheses are described in Italics*):

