- Chronic ischemic heart disease with unstable angina, chronic heart failure class III or IV, and myocardial infarction in the last 6 months
- Chronic diarrhea
- Type I diabetes mellitus
- Pituitary dwarfism
- Medication use
 - Current use of digoxin and licorice
 - Current use of blood anticoagulant drugs such as Dicumarol (Warfarin), Clopidogrel (Plavix), Prasugrel HCl (Effient), Ticlopidine (Ticlid), Lovenox (Enoxaparin), Fragmin (Dalteparin), Innohep (Tinzaparin), Eptifibatide (Integrilin), Tyrofiban (Aggrastat), and Abciximab (Reopro)
 - Current use of lithium carbonate therapy (Eskalith, Lithobid, Lithonate, Lithotabs, Apo-Lithium carbonate, Apo-Lithium carbonate SR, Carbolth, Duralith, PMS-Lithium carbonate, PMS-Lithium citrate)
- Individuals with a history of colon resection or colectomy due to any reason
- Individuals with any history of cancer other than non- melanoma skin cancer
- Individual with history of any organ transplantation

- Individual with history of gastric bypass due to any reason
- Individuals with any history of cancer other than non- melanoma skin cancer
- Individuals with Inflammatory bowel disease

4. PPCCT research staff will mail a recruitment letter describing study and invitation to potential participants.

- Mail eligible candidates an introductory letter from the parent study PI (Appendix B) and another introductory letter from the current study PI and the gastroenterologist (Appendix B) describing the study and inviting them to participate.
- A study project telephone number and email address are included with the recruitment letter.
- Letters will be mailed in waves such that 50% of candidates carry the GG genotype and the other 50% possess the GA or AA genotype. We will repeat this procedure with subsequent waves until 120 with the GG genotype and 120 with either the GA or AA genotype complete the study process.
- In the meanwhile the introductory letters will be sent to the potential participants by email.

5. PPCCT research staff will place a follow-up phone call (RECRUITMENT ELIGIBILITYFORM 3, Appendix B) beginning seven days after the letter is sent to answer questions, evaluate interest and determine the participants' potential eligibility.

- Attempts will be made to telephone each participant for the purposes of recruitment
 - Attempt includes leaving a message on an answering machine or with a household member to call regarding study.
- Answer questions about the study

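### The 65% power for the treatment-by-AA interaction counts all ten AA carriers as analysed; at the loss implied by the plan's own enrolment and completion targets it is about 55–60%.

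*Combined protocol and SAP*

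**What the plan says.** Section 9.0 (power analysis) sizes the trial on erythrocyte magnesium in a 2 by 2 layout, GG versus GA/AA by treatment versus placebo: "There are 4 groups with 60 patients each by study design". For that layout, "At a 5% two-sided significance level, a two-way analysis of variance will have 94% power to detect the main treatment effect", and the same figure is given for the interaction; it drops to 71% at the larger standard deviation of 1.16.

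The section then turns to three genotypes. For AA carriers the investigators "expect to recruit 10 subjects during the 4 year recruiting period", five to be randomised to each arm. A simulation addresses two contrasts, namely "the interaction between the treatment and the GA genotype and the interaction between the treatment and the AA genotype", both taken against GG. Its result reads: "The power is 68% and 65%, respectively, with alpha=0.05".

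On numbers enrolled, Section 2.0 has 152 GG participants and "136 who possess at least one variant A allele (i.e. either GA or AA genotype), 10 of whom carry the AA genotype". The Protocol Summary in Section 6.0 repeats this. On numbers finishing, the recruitment procedure in Section 6.0 (part B, step 4 for participants from the earlier adenoma studies) sends letters until 120 GG and "120 with either the GA or AA genotype complete the study process".

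**The concern.** The ten AA carriers are a count at enrolment and randomisation, while the 60-per-cell layout of the power calculation matches the number of completers. The GG and carrier totals are inflated for loss (152 for 120, and 136 for 120). The AA count is not: ten are enrolled and ten are analysed.

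With five people per arm, almost all the variance of the AA contrast comes from those ten people, so losing one or two matters. Carriers who drop out are replaced until 120 complete, but the plan puts the AA frequency at 1.6%, so a replacement is unlikely to be AA.

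At stake is how a reader will take a non-significant treatment-by-AA interaction. The plan regards AA carriers as likely to benefit most, so the chance of missing the assumed effect should be stated correctly.

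**Working it through.** **Inputs**
- Placebo means from Table D3: GG 5.25, GA 4.61, AA 3.70 mg/dL (the AA value comes from one patient). Section 9.0 sets the treated mean at 5.25 for every genotype.
- Treatment effects are therefore 0 (GG), 5.25 − 4.61 = 0.64 (GA) and 5.25 − 3.70 = 1.55 (AA).
- Completers per arm: 60 GG and 60 carriers. I take the five AA as part of the 60, leaving 55 GA.
- Alpha 0.05, two-sided. Sidedness is stated for the 2 by 2 calculation and assumed for this one.
- Standard deviations (SDs): Section 9.0 says they differ by subgroup in the simulation. Table D3 prints placebo values (1.16 GG; 0.40 GA, borrowed for AA). Treated-arm values are not printed.

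**Step 1. Reproduce the 2 by 2 figures.** The interaction is 5.25 − 4.49 = 0.76, with SE = SD × √(4/60).
- SD 0.83: SE 0.214, ratio 3.55, power 94.2% (stated 94%).
- SD 1.16: SE 0.300, ratio 2.54, power 71.5% (stated 71%).

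**Step 2. Reproduce 68% and 65%.** For genotype g against GG with a common SD and equal arms, SE = SD × √(2/60 + 2/n_g), where n_g is the number per arm. Power comes from the noncentral t distribution with 240 − 6 = 234 degrees of freedom. Solving for the SD that gives 68% for GA yields 0.994.
- GA: SE = 0.994 × √(2/60 + 2/55) = 0.262; 0.64/0.262 = 2.44; power 68.0%.
- AA: SE = 0.994 × √(2/60 + 2/5) = 0.654; 1.55/0.654 = 2.37; power 65.5%.

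One SD thus recovers both stated figures, with all ten AA carriers included.

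**Step 3. Apply the plan's own loss.** Carrier loss is (136 − 120)/136 = 11.8%. If AA carriers are lost at the same rate, 10 × 120/136 = 8.8 remain, or 4.4 per arm.
- 4.4 per arm: SE = 0.994 × √(2/60 + 2/4.4) = 0.694; ratio 2.23; power 60.4%.
- One lost per arm (4 each): SE = 0.994 × √(2/60 + 2/4) = 0.726; ratio 2.14; power 56.6%.

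The chance that none of the ten is lost is (120/136)^10 = 29%. At the overall loss of 48/288 = 16.7% it is (240/288)^10 = 16%.

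**Step 4. Vary the unprinted SDs.** Rows 2 to 4 are simulations; n per arm is GG/GA/AA.

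| SD assumption | GA, none lost | AA, none lost | AA, one lost per arm |
|---|---|---|---|
| Common 0.994; 60/55/5 | 68.0% | 65.5% | 56.6% |
| Treated carriers 1.16, placebo carriers 0.40, GG 1.16; 60/60/5 | 67.7% | 64.8% | 55.2% |
| As row 2; 60/55/5 | 65.4% | 64.5% | 55% |
| Table D3 SDs in both arms; 60/55/5 | 79.7% | 89.6% | 80% |

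The first two rows recover the stated pair and the third nearly does. The fourth does not, so it cannot be what the plan simulated.

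**Step 5. An allele-count term, for comparison.** With 60/55/5 per arm the mean count is 65/120 = 0.542 and Sxx = 75 − 120 × 0.542² = 39.8. The slope of effect on count is [50.7 − 0.542 × 42.95]/39.8 = 0.69, where 50.7 = 55 × 0.64 + 10 × 1.55 and 42.95 = 55 × 0.64 + 5 × 1.55. SE = 0.994 × √(2/39.8) = 0.223; ratio 3.09; power 86.9%. Across the first three rows of the table the range is 85–87%. Under other response patterns at SD 0.994:
- Only AA responds: about 25%, against 65% for the AA contrast.
- Only GA responds: 44%, against 68% for the GA contrast.
- Both effects 0.64: 65%, against 70% for GG versus carriers.

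**The case against.** The loss among AA carriers is inferred; the plan states no rate for them. Section 6.0 (part G) predicts low drop-out, and Aim 2 mentions about ten AA carriers while describing the 60-per-cell arms, which could be read as ten completers. At 4.4 per arm the drop is only about five points. The analysis is also secondary to the carrier comparison, and the plan already estimates the AA effect with a 95% confidence interval. This limits the importance of the point but does not remove it: Section 2.0 explicitly places the ten among the 136 enrolled, and Section 9.0 speaks of recruiting and randomising them.

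A reader might go further and infer three things that the documents do not support.
- **That the plan will decide the three-genotype question by two separate contrasts.** Those contrasts describe the power simulation. The data analysis plan says only that interactions will be tested, with genotype in two or three groups, and leaves the form of the test open.
- **That Aim 2 as a whole has only 65–68% power.** Aim 2 is built and sized on GG versus GA/AA, at 94% (71% with the larger SD).
- **That an allele-count test should replace the contrasts.** Its advantage depends on near-linear effects, and the AA end of that line is one pilot patient. Step 5 shows what it loses under other patterns. Against a rule that counts either contrast as a success (84–86%, unadjusted) it gains little power; its benefit is a 5% error rate in place of roughly 7–10%.

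**Conclusion.** The stated 65% holds only if all ten AA carriers recruited are analysed, and the plan's enrolment and completion targets do not deliver that. A fair figure is about 60% at the implied 11.8% loss and 55–57% with one AA carrier lost per arm.

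This rests on four assumptions: AA carriers are lost at the same rate as carriers generally; the SDs are ones that recover or nearly recover 68% and 65%, since the actual ones are not printed; the ten AA are the number enrolled, as Section 2.0 says; and the pilot AA mean of 3.70 is taken at face value. The figures apply to erythrocyte magnesium only and say nothing about power for the mucosal markers.

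The correction is modest. It concerns one stated power for a supplementary comparison and does not show that the design or the two-group interaction test is inadequate.

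**What to change.** In Section 9.0:
- Restate the power for the treatment-by-AA interaction as about 55–60%.
- Print the SDs used in the simulation for each genotype and arm, and the number of AA completers assumed.
- Say that the AA result will be read mainly as an estimate with its 95% confidence interval, which the data analysis plan already produces.

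Optionally, name a treatment-by-allele-count term as a supplementary analysis, noting that its 85–87% power depends on near-linear effects. It should not be made the single three-genotype test.

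The cost is a few lines of text and one rerun of the existing simulation. No additional participants or data are needed.
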